1.2 STUDY FLOW CHART

Day (D)/Week (W)/ Month (M)	W0 (End of DB treatment visit parent study) ^C (D1)	W 4	W 8	W 12	W 24	W 36	W 48	W 60	W 72 M18	W 84	W 96 M24	W 108	W 120 M30	W 132	W 144 M36	W 156	W 168 EOT 2Q 2017 M40	W176 EOS Call***
Visit Number	1	2	3	4	5	6*	7	8*	9	10*	11	12*	13	14*	15	16*	17	18
Visit Window (days)		±7	±7	±7	±7	±7	±7	±7	±7	±7	±7	±7	±7	±7	±7	±7	±7	±7
Design																		
Informed consent	Χa																	
Patient demography	Х																	
Inclusion/Exclusion Criteria	Χa																	
Physical examination	Х	Х		Х	Х		Х		Х		Х		Х		Х		Х	
Body weight	Х	Х		Χ	Х		Х		Х		Х		Χ		Х		Х	
IVRS/IWRS contact	Χa			Χ	Х	Х	Х	Х	Х	Х	Х	Χ	Х	Х	Х	Х	Χ	Х
Treatment																		
Injection at site	Χa																	
Review of diet	Х						Х				Х				Х		Х	
Investigational Medicinal Product (IMP) kit dispensation	Xa			Х	Х	Х	Х	Х	Х	Х	Х	Χ	Х	Х	Х	Х		
Compliance check of IMP (review patient diary ^e and treatment kit) and data collection on IMP administration	X (diary ^a)	X (diary only)	X (diary only)	Х	Х	Х	Х	Х	Х	Х	Х	Х	Х	Х	Х	Х	Х	
Concomitant medication	Х	Х	Х	Х	Х	Х	Х	Х	Х	Х	Х	Χ	Х	Х	Х	Х	Х	Х

Day (D)/Week (W)/ Month (M)	W0 (End of DB treatment visit parent study) ^C (D1)	W 4	W 8	W 12	W 24	W 36	W 48	W 60	W 72 M18	W 84	W 96 M24	W 108	W 120 M30	W 132	W 144 M36	W 156	W 168 EOT 2Q 2017 M40	W176 EOS Call***
Visit Number	1	2	3	4	5	6*	7	8*	9	10*	11	12*	13	14*	15	16*	17	18
Visit Window (days)		±7	±7	±7	±7	±7	±7	±7	±7	±7	±7	±7	±7	±7	±7	±7	±7	±7
Vital signs																		
Heart rate, blood pressure	Х	Х	Х	Χ	Х		Х		Х		Х		Х		Х		Х	
Safety																		
AE / SAE recording	Х	Χ	Χ	Χ	Х	Х	Х	Х	Χ	Χ	Χ	Χ	Χ	Χ	Χ	Χ	Х	Х
Central Laboratory Testing – Efficacy																		
Total-C, calculated LDL-C, HDL-C, TG, non-HDL-C	Х		Х		Х		Х		Х		Х		Х		Х		Х	
Apo B, Apo A-1, ratio Apo B / Apo A-1, and Lp (a)	Х						Х				Х		¥		Χ		Х	
Laboratory Testing – Safety																		
Central Hematology and chemistry	Х		Х		Х		Х		Х		Х		X		Х		Χ	
Central Creatine phosphokinase (CPK)	Х		Х		Х		Х		Х		Х		Х		Χ		Х	
Central Liver panel	Х	Х	Х	Χ	Х		Х		Х		Х		Χ		Χ		Х	
Local Urine pregnancy test	Xp	Х	Х	Χ	Х		Х		Х		Х		Χ		Χ		Х	

Day (D)/Week (W)/ Month (M)	W0 (End of DB treatment visit parent study) ^C (D1)	W 4	W 8	W 12	W 24	W 36	W 48	W 60	W 72 M18	W 84	W 96 M24	W 108	W 120 M30	W 132	W 144 M36	W 156	W 168 EOT 2Q 2017 M40	W176 EOS Call***
Visit Number	1	2	3	4	5	6*	7	8*	9	10*	11	12*	13	14*	15	16*	17	18
Visit Window (days)		±7	±7	±7	±7	±7	±7	±7	±7	±7	±7	±7	±7	±7	±7	±7	±7	±7
Laboratory Testing – Other																		

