6.2 DURATION OF STUDY PARTICIPATION

6.2.1 Duration of study participation for each patient

The OLE study is planned to be completed in second quarter 2017 which corresponds to a study duration of approximately 168 weeks for the first patients enrolled or until the drug is commercially available for the patient in the respective country, whatever comes first. For patients in the UK, the study will last a maximum of 176 weeks.

The study duration includes up to approximately 3.5 years of treatment for the first patients enrolled, and 10 weeks of follow up after the last IMP injection for all the patients, those who will complete the study and those who will early discontinue whatever the reason.

The study will be considered as completed for a patient in the following situations:

- When the alirocumab is commercially available in the patient's country
- In second quarter 2017, if alirocumab is not yet commercially available in the patient's country

An EOT visit will be done 2 weeks after the last IMP injection and a safety follow up call 10 weeks after the last IMP injection.

The following situations will be considered as premature discontinuation of the patient from the study:

- Any withdrawal from the study to switch to an anti-PCSK9 inhibitor different from commercial alirocumab
- Any other reason

An unscheduled visit should take place within 5 days after the last IMP administration if possible, with assessments normally planned at the EOT visit, and a safety follow up call performed 10 weeks after the last IMP injection (see section 10.3.4).

The end of study per patient is the last protocol planned call. Patients with a Serious Adverse Events (SAEs) or an Adverse Event of Special Interest (AESI) should be followed until resolution, stabilization, or death.

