10.1.1.17 End-of-treatment visit: Visit 17/ Week 168/ Month 40 (Day 1177± 7)

The end of study is scheduled to be in second quarter 2017 or when the drug will become commercially available for the patient in the respective country whatever comes first. Thus, the End-of-treatment visit might be performed earlier than on Week 168 according to the date of inclusion of each patient in the OLE study, or if the patient early discontinues the study.

- Collect adverse events
- Record concomitant medication
- Take vital signs including heart rate and blood pressure
- Get body weight measurement
- Physical examination
- Review patient's diet. Patient should be on a NCEP-ATPIII TLC diet or equivalent.
- Data collection on IMP administration and IMP compliance check by review of diary and treatment kit
- IVRS/IWRS contact to document the end of treatment
- Obtain fasting blood sample for:
 - Lipids: measure and/or calculation of total-C, LDL-C, HDL-C, TG, non-HDL-C, Apo B, Apo A-1, ratio Apo B/Apo A-1, and Lp (a)

- Hematology
- Chemistry
- CPK
- Liver panel
- Anti-alirocumab antibodies

- Local urine pregnancy test (females of childbearing potential only).
- Completion of EQ-5D questionnaire by patient.
- Reminders
 - For all the patients, those who prematurely discontinue the treatment irrespective of the reason and those who will complete the study, an appointment will be given for the Follow up call. This phone call will have to be scheduled 10 weeks after last injection (+/- 7 days).

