# 1 OVERVIEW AND INVESTIGATIONAL PLAN

#### 1.1 STUDY DESIGN AND RANDOMIZATION

This is a Phase 3, multicenter, multinational, open-label extension (OLE), uncontrolled study that includes patients diagnosed with heterozygous familial hypercholesterolemia (heFH) who have completed one of the four randomized, double-blind, 18-month parent studies: EFC12492 (ODYSSEY FH I), R727-CL-1112 (ODYSSEY FH II), EFC12732 (ODYSSEY High-FH) or LTS11717 (ODYSSEY long term).

The first study visit (Visit 1 on Day 1) of the OLE study takes place at the end of treatment (EOT) visit for patients enrolled in EFC12492, R727-CL-1112 and EFC12732 studies, or at the end of study (EOS) visit for those enrolled in the LTS11717 study.

All patients receive alirocumab 75 mg every 2 weeks (Q2W) at entry into the OLE, with the exception of patients from EFC12732 who receive 150 mg Q2W, as in the parent study. From Day 1 (Visit 1) to Week 8 (first unblinded LDL-C value), neither the treatment received at the end of double-blind treatment period of the parent study, nor the lipid parameters level, will be known by the investigator or by the patient, in order to prevent any potential blinding breaking of the parent study. From Week 12 (Visit 4), the investigator may manage adjustment of alirocumab doses (uptitration from 75 mg to 150 mg Q2W, down-titration from 150 mg to 75 mg Q2W or maintenance of dose), based on his/her own judgment and LDL-C values. Patients are to be treated for up to 168 weeks ie approximately 3.5 years with alirocumab, for the first patients enrolled, or until the product becomes commercially available for the patient in the country, whatever comes first. All patients are to be followed by phone 10 weeks after last investigational medicinal product (IMP). Patients with a Serious Adverse Events (SAEs) and or an Adverse Event of Special Interest (AESI) should be followed until resolution, stabilization, or death.

Up to approximately 1,200 heFH patients were estimated to be enrolled from approximately 200 sites worldwide.

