# Up-Titration/Down-Titration/maintenance of dose

The number (%) of patients with an up-titration to 150 mg/down-titration to 75 mg/maintenance of 75 mg/maintenance of 150 mg of alirocumab will be described overall and by visit, on the

Safety population. The number (%) of up-titration to 150 mg will also be summarized excluding patients coming from High FH study since these patients start the OLE study with this dose.

Reasons for up- or down-titration and LDL-C used to up/down-titrate or maintain 75/150 mg dose will be summarized, overall and by visit in order to get data about real life behavior of the investigator. LDL-C will be summarized quantitatively and with the following categories: <15,  $\ge 15$  and <25,  $\ge 25$  and <50,  $\ge 50$  and <70,  $\ge 70$  and <100,  $\ge 100$  mg/dL.

The LDL-C value and titration/maintenance of the current dose will be associated as follows:

- For each LDL-C value (calculated or measured, from central or local Lab), IVRS calls
  from x days after the sample date of this LDL-C to the sample date of the next LDL-C
  value (included) will be considered. In case several IVRS calls (for titration and for
  maintenance) are made during this time period, the selected LDL-C value will be
  associated to the titration call.
- x will depend on the minimum time needed for the availability of the LDL-C results to Investigators and will therefore be different for local lab (i.e. 1 day), calculated LDL-C from central lab (i.e. 3 days) and measured LDL-C from central lab (i.e. 7 days).
- In case no IVRS call is retrieved during the defined time period, the LDL-C value will be associated to maintenance of dose.

This analysis may also be done according to key factors (e.g. history of CV events at entry into the OLE study (Yes/No), geographical region) if the size of the subgroups permits.

In order to analyze the efficiency of the titration regimen to prevent low LDL-C compared to 150 mg administered throughout, the following analysis will be done in the subgroup of patients of the Safety population coming from LTS11717 study: number (%) of patients with 2 consecutive LDL-C <25 mg/dL during the OLE period (on titration regimen) will be compared to the number (%) of patients with 2 consecutive LDL-C <25 mg/dL during the double-blind period (on 150 mg). The same analysis will be done with 15 mg/dL threshold.

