# 3 INTERIM ANALYSIS

Interim analyses may be performed before the end of the study if requested by Health Authorities or if needed for the purpose of scientific communication.

Analyses methods and conventions described in the other sections of this SAP will be applied for all analyses as applicable. The following additional rules will apply for analyses performed at interim analysis:

- Patients without end of treatment visit performed at the time of the cut-off date will be considered as ongoing and exposed up to the cut-off date. Therefore:
  - Patients who did not complete treatment period nor prematurely discontinued the study treatment at cut-off date will be analyzed as "ongoing" in the disposition summary.
  - Their TEAE period, treatment period, efficacy treatment period and on-study observation period will end at the cut-off date.
  - Their treatment duration will be derived by considering date of cut-off as last injection date.
- Analyses of number of injections, mean injection frequency, percentage of days with under/above-planned dosing and compliance will be performed up to the last injection reported in the e-CRF up to the cut-off date.
- AEs occurring, worsening or becoming serious after the cut-off date will not be included in the analyses. However, any available outcome before database lock, regardless of timing in relation to the cut-off date, of an adverse event starting prior to the cut-off date will be taken into account. Medications, treatment discontinuations/completions and deaths occurring after the cut-off date will not be included in the analyses.
- Post-treatment period, post-study period are not applicable for ongoing patients. Analyses
  of post-treatment AEs, post-study deaths and post-treatment medications will be performed
  for patients who either completed or prematurely discontinued the treatment before or at
  the cut-off date.
- Analysis of proportion of patients with insufficient follow-up will be provided for patients
  who either completed or prematurely discontinued the treatment before or at the cut-off
  date.

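### The SAP's comparison of the titration regimen with 150 mg throughout uses whole-period percentages of low LDL-C, although the two periods differ in length and may differ in number of LDL-C samples

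*SAP*

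**What the plan says.** The subsection of SAP 2.4.3.1 on up-titration, down-titration and maintenance of dose sets out to assess how well titration avoids low LDL-C relative to 150 mg throughout. It says that "the following analysis will be done in the subgroup of patients of the Safety population coming from LTS11717 study". The outcome is a pair of successive LDL-C results under the 25 mg/dL threshold, and the percentage seen "during the OLE period (on titration regimen) will be compared to the number (%) of patients with 2 consecutive LDL-C <25 mg/dL" while taking 150 mg in the parent study. The exercise is repeated at 15 mg/dL. No common time window, censoring rule or matching of visits is given.

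The two periods are defined elsewhere:

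- **Double-blind.** Patients "have completed one of the four randomized, double-blind, 18-month parent studies" (SAP 1.1). SAP 2.4.4.2 uses a parent Week 78 value.
- **OLE.** Protocol 6.2.1 plans "approximately 168 weeks for the first patients enrolled or until the drug is commercially available for the patient in the respective country", whichever is first. Protocol 10.1.1.17 adds that "the End-of-treatment visit might be performed earlier than on Week 168 according to the date of inclusion of each patient in the OLE study".
- **Interim analysis.** For ongoing patients, SAP 3 states: "Their TEAE period, treatment period, efficacy treatment period and on-study observation period will end at the cut-off date".
- **OLE sampling.** The Protocol 1.2 flow chart row "Total-C, calculated LDL-C, HDL-C, TG, non-HDL-C" is marked, after Day 1, at Weeks 8, 24, 48, 72, 96, 120, 144 and 168.

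SAP 2.1.5 defines the low LDL-C event for the OLE: two consecutive calculated values at least 21 days apart. SAP 2.4.6 adds Kaplan-Meier curves from the first OLE dose, overall and by parent treatment.

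**The concern.** A patient counts once two consecutive low values have been seen at any time in the period. More time and more samples can only add patients, never remove them. When one period is nearly fixed and the other varies by patient, the difference between two such percentages mixes the effect of the regimen with the effect of being observed for longer or sampled more often.

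No other analysis in the SAP is stated to answer this question. The Kaplan-Meier curves in SAP 2.4.6 handle unequal follow-up within the OLE, but they are not specified for LTS11717 patients and have no double-blind counterpart in this SAP. The exposure table in SAP 2.4.3.1 also covers the OLE only. The same data could therefore seem to favour or disfavour titration according to the cut-off date or the sampling schedule.

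**Working it through.** The plan gives no expected percentage, sample size or power for this comparison, so there is no design figure to reproduce.

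**Durations.** 18 months × 365.25 / 12 / 7 = 78.3 weeks, which agrees with Week 78. The maximum ratio of OLE to double-blind follow-up is 168 / 78 = 2.15.

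**Scheduled OLE samples (flow chart).**

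| OLE follow-up | Samples | Consecutive pairs |
|---|---|---|
| Week 48 | 3 | 2 |
| Week 78 | 4 | 3 |
| Week 168 | 8 | 7 |

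A patient who stops early also has end-of-treatment lipids (Protocol 10.1.1.17 and 10.3.4), which adds one value. Someone ending around Week 60 would have 4 values, not 3. This does not help patients still ongoing at an interim cut-off.

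**Assumptions for illustration.** 20% of patients have the event by 78 weeks on 150 mg, and the regimens do not truly differ. Neither is a document figure.

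**Sample-count model.** Each LDL-C value is a stable patient level plus normal visit-to-visit error, with correlation r between visits. For a patient whose chance of a low value at any visit is q, the probability of no two consecutive low values in n samples follows a recurrence. Let a be the probability of no event so far with the last value not low, and b the same with the last value low. Start at a = 1, b = 0; at each sample, new a = (a + b)(1 − q) and new b = a·q. The event probability is 1 − (a + b) after n samples, averaged over patients. The cut-off is set to give 20% at the parent number of samples.

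| Parent samples | OLE samples | r = 0.9 | r = 0.7 | r = 0.5 |
|---|---|---|---|---|
| 4 | 3 (Week 48) | 17.8% | 16.4% | 15.6% |
| 4 | 8 (Week 168) | 24.0% | 27.4% | 30.4% |
| 6 | 4 (Week 78) | 17.8% | 16.2% | 15.1% |
| 6 | 8 (Week 168) | 21.5% | 22.7% | 23.7% |
| 8 | 4 (Week 78) | 16.5% | 14.1% | 12.4% |
| 8 | 8 (Week 168) | 20.0% | 20.0% | 20.0% |

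Every departure from 20% is artefact. With 4 parent samples a long OLE looks worse than it is. With 8, the bias at 168 weeks vanishes, and a 78-week window with 4 OLE samples shows a false benefit.

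**Lower end.** If all events occur early (say by Week 24), or LDL-C does not vary between visits (r = 1), the OLE shows 20% at 48 and at 168 weeks, so there is no bias.

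**Upper illustration.** Under a constant hazard, the OLE percentage at T weeks is 1 − 0.8^(T/78): 12.8% at 48 weeks and 38.2% at 168. Low LDL-C probably recurs in the same patients, so this overstates the effect.

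**Why patient-year rates do not solve it.** Suppose 20 of 100 patients have the event, all at Week 24, in both periods. Person-weeks are 20 × 24 + 80 × 78 = 6,720 and 20 × 24 + 80 × 168 = 13,920. The rate ratio is 6,720 / 13,920 = 0.48, although nothing differs.

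**The case against.** The strongest objection is that the obvious remedy, a common 78-week window, can be worse than the plan. The table bears this out: for patients followed to 168 weeks, with 6 or 8 parent samples, the whole-period comparison is closer to 20% than a 78-week window with 4 OLE samples. This stands. A common window must be combined with matched sampling in the main analysis.

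Three stronger readings are tempting, but the documents do not support them.

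- **That the plan is biased against titration.** The rows with 4 parent samples suggest it. For LTS11717, however, the SAP names only baseline, Week 8 and Week 78. For FH I and FH II, SAP 2.4.4.2 uses parent Weeks 8, 12, 24 and 78, which hints at sampling denser than the OLE's early on. The direction is open.
- **That the event is undefined.** The same subsection speaks of "For each LDL-C value (calculated or measured, from central or local Lab", but that bullet links LDL-C values to IVRS calls, a different task. SAP 2.1.5 defines the event, SAP 2.1.3 excludes measured LDL-C from calculated endpoints, and SAP 2.4.5.1 uses the same short form and refers back to 2.1.5. At most a cross-reference is missing.
- **That parent placebo patients are to be counted.** The subgroup wording does not exclude them, but the reference to 150 mg in the double-blind period points to the alirocumab arm. This needs clarification only.

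It is also fair that this is one descriptive summary in an uncontrolled extension, with no test or decision rule attached. And the parent SAPs are not available here, so only this SAP can be said to lack a matching double-blind analysis.

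**Conclusion.** The point holds and is minor. It is certain that SAP 2.4.3.1 compares whole-period percentages over periods of unequal and, on the OLE side, variable length, and that nothing in this SAP gives the two sides a common basis. The comparison can therefore mislead on its own stated aim, in either direction.

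Size and net direction cannot be determined without the LTS11717 sampling schedule and the realised OLE follow-up. In the sample-count model (20% assumed at 78 weeks, no true difference, 4 parent samples), the artefact runs from about 2 to 4 percentage points downward with 3 OLE samples to about 4 to 10 upward with 8. It is nil at 168 weeks with 8 parent samples, and could be near zero if events occur early. What is at stake is interpretation, not an error rate.

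**What to change.** In SAP 2.4.3.1, change the main comparison as follows:

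- **Window and visits together.** Within the same patients, use a common window from the first dose of each period, up to about 72-78 weeks, and matched LDL-C visits: the same or nearest nominal weeks and the same number of values per patient in both periods. The OLE offers Weeks 8, 24, 48 and 72. The LTS11717 weeks must come from that study's own schedule.
- **Estimate.** Give the Kaplan-Meier cumulative incidence at the end of the window, with censoring.
- **Event.** Cross-refer to SAP 2.1.5 for both periods (calculated LDL-C, at least 21 days apart), with both values inside the window, and apply the SAP 2.4.6 inclusion rule to both. Date the event at the first of the two values, as in 2.1.5, and state how a patient censored after a single low value is handled.
- **Reporting.** Show the number of LDL-C values per patient in each period.
- **Supportive only.** Keep the common-window estimate on all values and the whole-period percentages as supportive. Do not use patient-year rates for this comparison.
- **Clarification.** State that the subgroup is LTS11717 patients who received alirocumab in the parent study.

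The result stays descriptive. The cost is SAP wording and minor programming. OLE data after the window and unmatched samples leave this one comparison but remain in the SAP 2.4.6 analysis.

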Patients with heFH who cannot attain LDL-C goal despite lipid-modifying therapy, including a statin at maximally tolerated dose, present a high unmet need regarding their life-long increased cardiovascular risk. This study gives these heFH patients, who already participated in one of the double-blind 18-month ODYSSEY Phase 3 studies, the possibility to start or continue treatment with alirocumab after the end of the parent study. All patients will receive alirocumab at entry in the open-label extension study regardless of the study treatment they received during the 18-month double-blind treatment period of the parent study, provided they fulfill the eligibility criteria of the open-label extension study.

Description of the parent studies:

The study design of the four concerned parent studies was similar: Phase 3, 18-month treatment duration, randomized, double-blind, placebo controlled, parallel-group, multi-national, multi-center study.

They are briefly described in the table below.

Studies	EFC12492	R727-CL-1112	EFC12732	LTS11717	
	ODYSSEY FH I	ODYSSEY FH II	ODYSSEY High FH	ODYSSEY Long Term	
Patient population enrolled	Patients diagnosed with heFH, not adequately controlled with a maximally tolerated daily dose (MTD) of statin, stable for at least 4 weeks prior to the screening visit, with or without other lipid modifying therapy (LMT)				
Screening LDL-C at entry	≥ 70 with a history of documented cardiovascular disease		≥ 160	≥ 100	
(mg/dL)	≥ 100 without history of documented cardiovascular disease			(then ≥ 70, as per amendment 3, for about 10% of the heFH enrolled patients)	
				With or without documented cardiovascular disease	
Sample size	486	249	107	385	
(heFH patients actually randomized in the parent study)				(about 20% of all enrolled patients)	
Placebo or alirocumab dose at entry in parent study Q2W	75 mg		150 mg		
Double-blind treatment period duration	18 months				
Background LMT	MTD* statin (atorvastatin, rosuvastatin, simvastatin)				
	+/- other LMT				

- * Definition of Maximally Tolerated Dose (any of the following are acceptable):
- Rosuvastatin 20 mg or 40 mg daily
- Atorvastatin 40 mg or 80 mg daily
- Simvastatin 80 mg daily (if already on this dose for >1 year)

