11.4.3 Analyses of efficacy data

Efficacy variables will be explored through descriptive statistics at each scheduled visit of the current study.

Percent changes from baseline of the parent study and success rate to reach targets from week 8 time point will be analyzed all groups combined as influence of treatment received during the parent study should be offset by the treatment received during the current study after 8 weeks of treatment.

Percent changes, and when appropriate absolute change, from baseline of the parent study in calculated LDL-C, total-C, HDL-C, TG, and non-HDL-C will be summarized at each time point in the efficacy population using number of available data, mean, SD, median, minimum, and maximum. For percent change, 95% confidence intervals of the mean will also be provided. All measurements, scheduled or unscheduled, collected from week 8 up to 21days after the last IMP injection, will be assigned to analysis windows defined in the SAP in order to provide an assessment for these time points. Laboratory assessments other than the ones provided by the central laboratory will be excluded. For TG, measurements on not fasting patients will be excluded.

Same kind of tables (with either percent change from baseline or absolute change from baseline) will be provided for other efficacy parameters: Apo B, Apo A-1, ratio Apo B/Apo A-1, Lp(a).

For TG and Lp(a), summary statistics will include Q1 and Q3.

Success rate to reach the different targets defined for LDL-C in Section 9.2.1 will be provided with corresponding 95% confidence intervals.

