#### 2.3.2 Safety population

The Safety population considered for safety analyses will be the population who actually received at least one dose or part of a dose of the open-label IMP injection.

Enrolled patients for whom it is unclear whether they took the study medication will be included in the safety population.

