# 2.4.3 Extent of investigational medicinal product exposure and compliance

The extent of IMP exposure and compliance will be assessed and summarized for the safety population, overall as well as according to treatment received in the parent study (placebo versus alirocumab (regardless of dose)).

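### The low-LDL-C comparison in SAP 2.4.3.1 labels the LTS11717 double-blind period as 150 mg treatment, but its stated population includes former placebo patients

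*SAP*

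**What the plan says.** The titration part of SAP 2.4.3.1 sets out a comparison of the titration regimen with 150 mg given throughout.

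- **Population:** the "subgroup of patients of the Safety population coming from LTS11717 study".
- **Reference:** the "number (%) of patients with 2 consecutive LDL-C <25 mg/dL during the double-blind period (on 150 mg"). It is set against the same count in the open-label period, and both are repeated at 15 mg/dL.
- **Safety population (SAP 2.3.2):** "the population who actually received at least one dose or part of a dose of the open-label IMP injection". Enrolled patients whose intake is unclear are added. Parent-study arm plays no part.
- **Parent design (Protocol section 4):** each of the four parent studies, LTS11717 included, is described as a "randomized, double-blind, placebo controlled, parallel-group, multi-national, multi-center study".
- **Entry to the extension (Protocol section 4):** all eligible patients receive alirocumab "regardless of the study treatment they received during the 18-month double-blind treatment period of the parent study".
- **Display rule (SAP 2.4.3):** the "extent of IMP exposure and compliance will be assessed and summarized for the safety population", overall and by parent treatment (placebo or alirocumab).

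**The concern.** A former placebo patient from LTS11717 who takes one open-label dose belongs to the stated population, yet had no double-blind period on 150 mg. The sentence therefore names one group and describes another.

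The reference rate is the benchmark against which titration is judged. Patients who could hardly have an event under placebo would lower it, and titration would look less protective than it was. The question bears on safety, since the SAP also summarizes adverse events in patients with two consecutive values below 25 mg/dL. But it is descriptive and confined to one parent study.

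**Working it through.** The plan states no rate, power or sample size for this comparison, so there is no figure to reproduce. The check has three parts.

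**1. Does any other text supply the filter?**

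- SAP 2.4.3 gives a split, not a restriction, and names only exposure and compliance. The titration text that follows sets its own display (overall and by visit).
- SAP 2.4.6 splits by parent treatment, but for the endpoints of SAP 2.1.5. The proportions defined there are limited to the open-label treatment period, so they cannot define a double-blind reference.
- Where the titration text wants an exclusion it writes one: up-titration counts are repeated without High FH patients. It writes none here.

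No explicit filter was found.

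**2. How many events could placebo patients contribute?**

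The Protocol section 4 table gives screening LDL-C in LTS11717 as at least 100 mg/dL, later at least 70 "as per amendment 3, for about 10% of the heFH enrolled patients". The smallest fall needed without alirocumab is:

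| Threshold | From 100 mg/dL | From 70 mg/dL |
|---|---|---|
| <25 mg/dL | (100 − 25)/100 = 75.0% | (70 − 25)/70 = 64.3% |
| <15 mg/dL | (100 − 15)/100 = 85.0% | (70 − 15)/70 = 78.6% |

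The fall must show on two consecutive values. Almost no placebo events is a reasonable working assumption.

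**3. How far would the reference move under the literal, unsplit reading?**

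- f = placebo share among LTS11717 patients in the extension. Not in the documents; assumed 1/4, 1/3 or 1/2. The table gives 385 heFH patients randomized in LTS11717, both arms together. If all entered, these shares would mean about 96, 128 or 192 former placebo patients.
- q = double-blind event rate on placebo divided by that on alirocumab. Assumed 0, or 0.05 as a check.
- k = open-label event rate in former placebo patients divided by that in former alirocumab patients. Assumed 1 or 0.5. A value near 1 fits Protocol 11.4.3, where the "influence of treatment received during the parent study should be offset by the treatment received during the current study after 8 weeks of treatment", and SAP 2.4.4.2, which notes a 10-week washout before LTS11717 patients start the extension.

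Reference factor = (1 − f) + f·q.

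Inflation of the ratio (open-label rate over 150 mg rate) = [(1 − f) + f·k] / [(1 − f) + f·q].

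| | f = 1/4 | f = 1/3 | f = 1/2 |
|---|---|---|---|
| Reference factor, q = 0 | 0.750 | 0.667 | 0.500 |
| Reference factor, q = 0.05 | 0.762 | 0.683 | 0.525 |
| Ratio inflation, q = 0, k = 1 | 1.333 | 1.500 | 2.000 |
| Ratio inflation, q = 0, k = 0.5 | 1.167 | 1.250 | 1.500 |
| Ratio inflation, q = 0.05, k = 1 | 1.311 | 1.463 | 1.905 |

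Inflation exceeds 1 exactly when k > q: relative to alirocumab patients, former placebo patients must have a higher event rate in the extension than they had on placebo.

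A filter on the double-blind side only would multiply the ratio by (1 − f) + f·k. With k = 1 that is 1. With k = 0.5 it is 0.875, 0.833 or 0.750, an error in the opposite direction. Both sides need the same patients.

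**The case against.** The strongest reply is that the sentence restricts itself. Its aim is a contrast with 150 mg given throughout, and its reference period carries the 150 mg label. A placebo patient has no such period. The documents also often name a parent study when they mean its active arm. The dose rationale in Protocol section 4 says patients in LTS11717 and EFC12732 were started on 150 mg. SAP 1.1 says EFC12732 patients receive 150 mg as in the parent study. SAP 2.4.4.2 describes LTS11717 patients as all having received 150 mg. And the SAP splits most of its analyses by parent treatment, so an alirocumab column may well be produced here too.

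Much of this stands. It shows what was intended, and makes a correct analysis in practice quite possible. It does not make the written population right: a programmer who follows it literally gets a mixed reference, and one who infers a filter must still choose whether it covers one side or both.

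Three stronger readings are tempting, and the documents support none of them.

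- *The 150 mg rate will be diluted.* This requires both the literal population and no split by parent treatment. The label and aim point the other way.
- *The comparison would reverse.* An assumed true ratio of 0.60 would appear as 0.60 × 2.00 = 1.20, but only with f = 1/2, k = 1 and q = 0 together. All four values are assumptions. This illustrates the algebra and does not estimate this trial.
- *SAP 2.4.4.2 has the same defect.* Its clause on 150 mg can be read as limiting the group to alirocumab patients. No bias follows from it.

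**Conclusion.** The point holds as a mismatch between the stated population and its label. Confidence in that is high. Confidence that the reported result would be diluted in practice is medium, because the intent is fairly clear and the split by parent treatment may be applied.

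Under the literal, unsplit reading with almost no placebo events, the 150 mg reference is multiplied by about 1 − f: 0.75 to 0.50 for an assumed f of 1/4 to 1/2. A benefit of titration is then understated provided k > q. With the split, the alirocumab column is right and only the overall column is mixed. No test, error rate or primary safety result depends on the comparison. Severity: minor.

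**What to change.** In the titration text of SAP 2.4.3.1, define the group for this comparison as Safety-population patients from LTS11717 who received alirocumab in the double-blind period. State that the restriction applies to both the open-label and the double-blind count, and to both the 25 and the 15 mg/dL threshold. SAP 2.4.4.2 needs no change for this point.

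The cost is one line of text and one filter on parent treatment, a variable the SAP already uses throughout. Fewer patients enter this one comparison: if all 385 had entered, about 289, 257 or 192 would remain for f = 1/4, 1/3 or 1/2. In return, the same patients are compared on 150 mg and on the titration regimen.
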